3.8.2 Eligible hospitals

Existing capacity to provide the following services: acute paediatric care services 24/7 covered by medical and nursing staff, radiology service, capacity to administer intravenous fluids and antibiotics and basic pathology or standard remote pathology services (point-of-care).

3.8.3 Exclusion Criteria

There are no formal patient exclusion criteria as the intent of the study is to observe and monitor all episodes when a child presents with acute respiratory failure (including bronchiolitis) to one of the participating hospitals.

4. STUDY DESIGN

4.1. Type of Study

A stepped wedge cluster-randomised study design will be used to investigate evaluation of the structured implementation of a respiratory care bundle (the intervention) for paediatric ARF including bronchiolitis in rural and remote hospitals in North Queensland. A stepped wedge design is a type of crossover design in which different clusters cross over from the control group to the intervention group at different time points. All clusters are measured at each time point (Figure 2). The first time point corresponds to a baseline measurement where none of the clusters receive the intervention of interest; at the last time point all clusters receive the intervention. After intermediate time points, clusters initiate the intervention. A transition period of one month will occur prior to intervention phase for medical and nursing staff to receive education. More than one cluster may start the intervention at a time point, but the time a cluster begins the intervention is randomised. This way, both comparisons between units and within units are possible, making the design powerful. [15, 16] There will be no individual clinical participant randomisation for this trial design.

Cluster	Site	2023				2024												2025												2026		
		Sep	Oct	Nov	Dec	Jan	Feb	Mar	Apr	May	Jun	Jul	Aug	Sep	Oct	Nov	Dec	Jan	Feb	Mar	Apr	May	Jun	Jul	Aug	Sep	Oct	Nov	Dec	Jan	Feb	Mar
		1	2	3	4	5	6	7	8	9	10	11	12	13	14	15	16	17	18	19	20	21	22	23	24	25	26	27	28	29	30	31
1	1	C	C	C	C	C	C	T	I	I	I	I	I	I	I	I	I	I	I	I	I	I	I	I	I	I	I	I	I	I		
	2	C	C	C	C	C	C	T	I	I	I	I	I	I	I	I	I	I	I	I	I	I	I	I	I	I	I	I	I	I		
	3	C	C	C	C	C	C	T	I	I	I	I	I	I	I	I	I	I	I	I	I	I	I	I	I	I	I	I	I	I		
2	4	C	C	C	C	C	C	C	C	C	C	C	C	C	T	I	I	I	I	I	I	I	I	I	I	I	I	I	I	I		
	5	C	C	C	C	C	C	C	C	C	C	C	C	C	T	I	I	I	I	I	I	I	I	I	I	I	I	I	I	I		
	6	C	C	C	C	C	C	C	C	C	C	C	C	C	T	I	I	I	I	I	I	I	I	I	I	I	I	I	I	I		
	7	C	C	C	C	C	C	C	C	C	C	C	C	C	T	I	I	I	I	I	I	I	I	I	I	I	I	I	I	I		
	8	C	C	C	C	C	C	C	C	C	C	C	C	C	C	C	C	C	C	T	I	I	I	I	I	I	I	I	I	I	I	
3	9	C	C	C	C	C	C	C	C	C	C	C	C	C	C	C	C	C	C	T	I	I	I	I	I	I	I	I	I	I		
	10	C	C	C	C	C	C	C	C	C	C	C	C	C	C	C	C	C	C	T	I	I	I	I	I	I	I	I	I	I		
	11	C	C	C	C	C	C	C	C	C	C	C	C	C	C	C	C	C	C	T	I	I	I	I	I	I	I	I	I	I		
4	12	C	C	C	C	C	C	C	C	C	C	C	C	C	C	C	C	C	C	C	C	C	C	C	C	T	I	I	I	I		
	13	C	C	C	C	C	C	C	C	C	C	C	C	C	C	C	C	C	C	C	C	C	C	C	C	C	T	I	I	I	I	
	14	C	C	C	C	C	C	C	C	C	C	C	C	C	C	C	C	C	C	C	C	C	C	C	C	C	T	I	I	I	I	

Stepped wedge cluster randomised design

- Performed across 31 months with 4 clusters of 3-4 hospitals randomised at each step with 6-month intervals
- C – Cluster unexposed to intervention (Control phase) → collection of data from all levels (service, health providers, parents/caregivers)
- T – Cluster in transition period while health providers receive training
- I – Cluster exposed to intervention (Intervention phase) → collection of data from all levels (service, health providers, parents/caregivers)

* Data will be captured over the entire duration of the study including Control and Intervention phases which includes:

(a) Service – Clinical data; (b) Health providers and Parents/Caregivers - Health Economy and Implementation Science data.

* Intervention is the *Implementation of the Respiratory Care Bundle*

Figure 2 – Stepped Wedge Cluster-randomised study design

Because the design ensures that all participants receive the intervention before the end of the study, it is especially useful for interventions with elements that have been shown to be effective in explanatory research. Conducting the intervention in all participants is an important ethical consideration for interventions that are believed to be superior compared to the control condition, and this may increase the motivation for participating in the study. Gradual crossing over to the intervention condition will occur, which is inherent to the

stepped-wedge design, and may, in fact, provide additional information about the influence of contextual changes. Because the period of the intervention varies per group, researchers can account for the interaction effect of different time points with changing context and the duration of the intervention.

Additionally, the sequential introduction of the respiratory care bundle allows a more efficient allocation of the research resources. Simultaneous introduction of the bundle in the context of the rural and remote hospitals is logistically difficult (distance, staff shortages, local governance processes).

4.2. Study Setting

14 rural and remote North QLD hospitals who provide 24/7 nursing and medical acute care for infants and children and are linked with RSQ and RFDS services to a metropolitan/tertiary hospital in Cairns or Townsville.

Sites include:

Hospital Health Service (HHS)	Hospital	Clinical Services Capability Framework level of paediatric emergency service	Clinical Services Capability Framework level of paediatric medical inpatient service
Torres and Cape HHS	Weipa Hospital	Nil for ED	2
	Thursday Island Hospital	Nil for ED	2
	Cooktown Hospital	Nil for ED	2
	Bamaga Hospital	Nil for ED	2
North West HHS	Mt Isa Base Hospital	4	4
	Cloncurry Hospital	Nil for ED	2
	Doomadgee Hospital	Nil for ED	2
	Normanton Hospital	Nil for ED	2
	Mornington Island Hospital	Nil for ED	2
Cairns and Hinterland HHS	Atherton Hospital	Nil for ED	2
	Innisfail Hospital	Nil for ED	2
	Mareeba Hospital	Nil for ED	2
	Mossman Hospital	Nil for ED	2
	Tully Hospital	Nil for ED	2

4.2.1 Site requirements:

- Acute paediatric care services 24/7 covered by medical and nursing staff according to the local CSCF level
- Radiology service as part of standard service delivery

- Capacity to administer intravenous fluids and antibiotics
- Basic pathology or standard 'point-of-care' remote pathology services as part of standard service delivery
- Compliance with all requirements of the acute paediatric respiratory care bundle as part of standard service delivery

4.2.2 Site responsibilities:

- Identify a Principal Investigator (PI) to lead the trial within the health district
- Identify a doctor and nurse/allied health professional champion in each hospital
- Agree to incorporate the study into routine paediatric acute care clinical practice,
- Highlighting the importance of adherence to the bundle within the boundaries of best clinical care
- Agree to optimally monitor and document clinical care as part of standard service delivery
- ***No Good Clinical Practice (GCP) training is required*** for this trial design

The following must be in place prior to a site being activated for implementation:

- A complete site initiation visit (pending COVID-19 restrictions)
- all relevant institutional approvals (e.g. local confirmation of capacity and capability)
- Governance approval, which is preceded by local community engagement (site specific)
- Fully signed Clinical Trial Site Agreement
- Fully signed Delegation Log

Once the overarching lead Chief Investigator of this study has confirmed that all necessary approvals and documentation is in place, a site activation email will be issued to the local research team, at which point, the site may start the Implementation process (phase II). Once the site has been activated, the local research team is responsible for ensuring:

- Adherence with the most recent approved version of acute paediatric respiratory care bundle
- Training of relevant site staff in accordance with the trial protocol and, if overseeing the study, Good Clinical Practice (GCP) requirements
- Timely data collection, entry and validation; and
- Prompt notification of all adverse events.

All local staff (i.e. PI, local investigators, research teams) involved in the conduct of the trial must be trained to carry out their assigned roles. Site research staff should be signed off on the Delegation Log, once trained, and the Delegation Log should be copied and sent to the lead Chief Investigator whenever changes are made.

5. RECRUITMENT, RANDOMISATION AND CONSENT

5.1. Recruitment and randomisation

This project is a science implementation evaluation study implementing an existing clinical respiratory care bundle for children with ARF using a stepped wedge cluster randomised trial design. Each participating hospital is the unit of randomisation, and target for primary analysis. There is no individual participant randomisation required. Clinical indication will dictate medical care. The implementation start date will be randomly allocated to each hospital using a computer-generated sequence and using a stratification per hospital and health services (HHS). Therefore, no individual patient recruitment will occur, however outcome data of individual data of children presenting with and admitted/transferred with ARF obtained during and after the implementation will be used in comparison to historical data of children with ARF previously presented/admitted and/or retrieved at the participating hospitals. We therefore only seek a Public Health Act (PHA) approval to include all participating hospitals and enable the research team to collect and review patient information during the hospital admission period or where relevant data on transfer to higher level of care occurs. All individual patient data will be de-identified for the purpose of study analysis.

The study investigators will remain blinded to outcome data until the study database is locked for analysis.

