Data will be collected in an online REDCap database. In each site the emergency admissions will be screened for children 0-4 years of age presenting with respiratory symptoms. Data on the baseline demographics, physiology at presentation and initial medical management will be captured. Length of hospital stay, length of oxygen therapy, type of oxygen therapy, and amount of oxygen resources will be captured. Further information will be captured on methods of oxygen therapy. Adverse events will be recorded. For children who required transfer to high level of care, vital signs and clinical diagnosis and medical therapy provided at time of decision to transfer will be collected. Data on respiratory support during transfer, mode and length of transport and data on treatment in accepting hospital and length of hospital stay will be collected. Adherence to the respiratory care bundle will be measured by the number of frequency of deviations from the protocol.

Twelve parents per hospital using a face-to-face structured interview will complete a paediatric proxy health related quality of life measurer (PedsQL).

Historical Control. Admissions (HBCIS) to the participating hospitals in year 2016-2022 will be screened using the same screening log as in the main protocol (Year 2020-2022 will be separately analysed due to impact of COVID-19 pandemic) and the same data collection as above used.

Time Points for Data Collection. All physiological (heart and respiratory rate, temperature) and blood parameters (arterial gases) that are captured in the medical records during the hospital admission and where relevant during the transfer for higher level of care. If admitted to a tertiary hospital, data on respiratory support provided will be captured.

Specific data

The specific data set mirrors in its basic form the data captured in our previous 3 large RCT's using nasal high-flow in children with ARF or bronchiolitis. Additional data on out-of-pocket expenses and lost income will be recorded.

Background data:

Background data collection will be collected as per the CRF. Below outlines some of the specifics which continue the same data collection of the 3 large RCT's.

Demographics:

- Age (on admission)
- Gender
- Weight (on admission)
- Ethnicity
- Diagnosis at admission
- History and risk factors
 - Prematurity (<37 weeks at birth)
 - Previous neonatal respiratory support post delivery
 - Previous Intensive Care admission post delivery

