8.2 Data Analysis

Generalised linear mixed models (GLMMs) will be used to account for cluster hospital effects with adjustment for the rollout time of the intervention and potential district effect and estimate the change in the proportions of PICU transfers (using a logistic link function) as well as the length of stay in acute care settings (using Poisson or negative binomial distributions) under the intervention condition, compared with those under the control condition. Model fit and assumption testing will

be conducted as appropriate within the GLMM framework and significance will be set at $p < 0.05$. The GLMM can handle missing data in the outcome variable under the ignorable mechanism (such as missing completely at random).

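### Section 5.1 names historical data as the comparator, which contradicts the randomised control phase on which sections 4.1, 8.1 and 8.2 rest

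*Protocol*

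**What the plan says.** Section 5.1 describes the study as "using a stepped wedge cluster randomised trial design" and makes the hospital the unit of randomisation and of primary analysis. The same paragraph then states a comparison: outcome data from children seen during and after implementation "will be used in comparison to historical data of children with ARF previously presented/admitted and/or retrieved at the participating hospitals". The control phase is not mentioned there.

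Other sections describe a different comparison.

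- **Section 4.1:** "The first time point corresponds to a baseline measurement where none of the clusters receive the intervention of interest". The notes to Figure 2 define control-phase months and add: "Data will be captured over the entire duration of the study including Control and Intervention phases".
- **Section 8.1:** the sample size is 18 patients per hospital in each of five time points, with baseline recruitment counted in.
- **Section 8.2:** the mixed model is to "account for cluster hospital effects with adjustment for the rollout time of the intervention and potential district effect" and to estimate outcomes "under the intervention condition, compared with those under the control condition". It gives historical data no role.

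The historical set is a separate collection. Section 7.1, under a label that calls it a historical control, says: "Admissions (HBCIS) to the participating hospitals in year 2016-2022 will be screened using the same screening log". It adds that 2020-2022 will be analysed apart because of the pandemic. Section 3.4 defines the primary outcome against numbers under the pathways already in place, without saying when those numbers are collected.

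**The concern.** Randomising the crossover date protects the estimate only if intervention time is compared with control time from the same calendar period. If the comparator is children seen in 2016-2022, everything that changed between those years and September 2023 to March 2026 is credited to the bundle. The protocol itself gives reasons to expect change: it sets the pandemic years apart (7.1), and it reports that a pilot of a similar package has run since 2021 in three hospitals, with an initial fall in retrievals (2.3, 2.6). Sections 2.2 and 2.5 identify those hospitals, and section 4.2 lists all three as trial sites.

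An analysis written to 5.1 and one written to 8.2 would estimate different quantities. While both texts stand, a randomised estimate and a confounded one can each claim support from the protocol, and the choice could be made after the data are seen.

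**Working it through.** **1. Does the stated power need historical patients?**

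Inputs from section 8.1: 14 hospitals, 4 steps with 3 or 4 hospitals each, 18 patients per hospital per period, transfer rates of 25% and 12.5%, intracluster correlation 0.1, two-sided 5%. The baseline plus 4 steps give 5 periods. The split 3, 4, 4, 3 is read from Figure 2, whose layout is imperfect in the available text.

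- Patients: 14 × 5 × 18 = 1,260, the stated total.
- Months: 31 − 1 transition = 30 = 5 × 6, so the five periods already leave the transition month out.

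Hussey and Hughes variance, with s² the within-hospital variance divided by m = 18, and t² the between-hospital variance:

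Var = I·s²(s² + T·t²) / [(I·U − W)s² + (U² + I·T·U − T·W − I·V)t²]

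- I = 14, T = 5.
- U = 3×4 + 4×3 + 4×2 + 3×1 = 35 intervention cells.
- W = 0² + 3² + 7² + 11² + 14² = 375.
- V = 3×16 + 4×9 + 4×4 + 3×1 = 103.
- Total variance at the control rate = 0.25 × 0.75 = 0.1875, so t² = 0.1 × 0.1875 = 0.01875 and s² = 0.9 × 0.1875 / 18 = 0.009375.
- Numerator = 14 × 0.009375 × (0.009375 + 5 × 0.01875) = 0.013535.
- Denominator = (490 − 375) × 0.009375 + (1,225 + 2,450 − 1,875 − 1,442) × 0.01875 = 115 × 0.009375 + 358 × 0.01875 = 7.7906.
- Var = 0.0017374, standard error 0.04168.
- Power = Φ(0.125 / 0.04168 − 1.96) = 85.06%.

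This matches the stated power of over 85%. Other conventions for the binary variance give 81.2% to 92.1%. None uses a historical patient.

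Control cells: 14 × 5 − 35 = 35, or 35 × 18 = 630 patients. Intervention cells: 35, or 630 patients. Half of the planned sample is the comparator that 5.1 does not mention.

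**2. Which comparator does each section support?**

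- Historical: 5.1 explicitly.
- Concurrent control: 4.1, 8.1 and 8.2.
- Open: 3.4. Section 8.1 uses nearly the same phrase for the 25% rate, which comes from 2016-2019 admissions but serves there as the control rate of a stepped wedge calculation. The phrase can be read either way.
- Open: 7.1, which calls the 2016-2022 set a control without saying what it is a control for.

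**3. What would a literal reading of 5.1 risk?**

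The drift values here are assumptions; the protocol gives none. Take 2,532 historical children (the 2016-2019 count in 8.1) at 25%, 630 intervention children, no bundle effect, and a simple two-proportion test that ignores clustering.

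| Assumed rate in trial years | Chance of a significant result |
|---|---|
| 25% (no drift) | 5% |
| 23% | 18% |
| 21% | 56% |
| 20% | 76% |
| 18% | 97% |

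Any drift passes one for one into the estimated difference.

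**The case against.** The strongest reply is that 5.1 does not set the analysis. The sentence explains why no patients are recruited and leads into the request for data access approval. It does not speak of a primary comparison or model. The sections that do fix the comparison all keep the control phase, and section 5.2 lists the historical set separately from the stepped wedge period. This reply stands against one stronger inference: a reader might conclude that 5.1 discards the randomised control phase and makes the trial an uncontrolled before-after study. The protocol does not support that, since design, power and model all depend on concurrent control months.

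A second reply is that the word implementation may cover the whole study. Section 7.2 and the milestones table after section 8.3 use it for all 31 months. On that reading the sentence compares the study period as a whole with history. This does not remove the conflict: the comparator is still historical, and control and intervention months would then sit on the same side.

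A third reply is that a supporting role for historical data can be left to the statistical analysis plan. That is fair for missing detail, but here the text states a comparator that conflicts with another section.

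A reader might also try to size the bias from the pilot. Halving the 108 bronchiolitis transfers per two years at those hospitals (216 over four) would take the overall rate from 633/2,532 = 25% to 525/2,532 = 20.7%. The halving is assumed, the four-year count is extrapolated, and 8.2 does not plan the analysis that would be biased. Nor can the pilot contaminate the 2016-2019 data: it began in 2021, within the years that 7.1 sets apart. A contrast in data source is also weak, because 7.1 screens emergency admissions in the trial and applies the same screening log and data collection to the historical set.

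**Conclusion.** The protocol contradicts itself on the comparator. Section 5.1 names historical data; 4.1, 8.1 and 8.2 use concurrent control periods; 3.4 and 7.1 do not settle which governs the primary outcome. Nothing in 8.1 or 8.2 is shown to be wrong, and the stated power is reproduced from in-trial patients alone, assuming the 3-4-4-3 split and total variance taken at the control rate.

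Following 5.1 would give an estimate confounded by calendar time. How large that bias would be cannot be derived from the protocol. The rejection rates of 18% to 97% rest on assumed drifts of 2 to 7 percentage points and a test that ignores clustering, so they show sensitivity and not an expected error. The point is a wording conflict, but it concerns the primary comparison and should be settled before outcome data are unblinded.

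**What to change.** - **Section 5.1:** replace the sentence. State that the primary comparison uses only prospectively collected control-phase and intervention-phase months of the stepped wedge (September 2023 to March 2026), with each hospital's transition month excluded.
- **Sections 5.1 and 7.1:** state that the 2016-2022 historical data and the April 2026 to April 2027 observational data are supplementary or descriptive and do not enter the primary model.
- **Section 3.4:** add that the comparator is care under the existing pathways during the randomised control phase.

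The cost is a few sentences, submitted to the ethics committee as an amendment under section 12. No data are lost, the historical collection can go ahead, and the sample size in 8.1 and the model in 8.2 are unchanged.

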5.2. Consent

For clarification of consent requirements see Figure 3.

- For children admitted to hospital with the diagnosis of ARF in the historical data set and in the data set of the observational period post the step wedged study period, we seek a waiver of consent. Contacting parents/guardians could be stressful considering there could have been a negative outcome. Such a burden of stress would not add any value to the study outcome. An informed consent process would also impose a selection bias of the analysed data as certain socio-economic groups will be unlikely to be willing to participate and difficult to approach due to frequent loss of contact post follow-up. Having robust processes in place guaranteeing data safety, deidentification and confidentiality, there is minimal risk imposed on the individual participant. No parent interviews will occur for these patients.
- During the step wedge phase of the study we seek a waiver of consent for patients admitted with ARF. This project aims to evaluate the implementation of an acute respiratory care bundle which is based on current best practice recommended by Queensland Health, hence a structured best evidence-based standardised approach to treat and manage acute respiratory failure in children. The project does not evaluate a new intervention nor a new care pathway. The intention is to streamline

the current QH Bronchiolitis guidelines, the current QH Asthma guidelines, the current QH Community Acquired Pneumonia (CAP) guidelines and the current Nasal High-Flow guidelines (all outlined on page 34 of the protocol).

- We will obtain written informed consent from parents of patients (n=12) for a parent interview per hospital in the control phase and n=12 in the implementation phase. The candidates for the interview will be indentified by the clinical team during hospital admission.
- Clinician interviews: we will use implied consent.

A Public Health Act (PHA) signed by all relevant Data Custodians will be required to access the childs health information data and deidentify for study purposes/collection.

[figure not shown]

Figure 3. Consent process aligned with Study Milestones (**Figure 4**)

